1.2.1. Darunavir (PREZISTA®)

Darunavir (formerly known as TMC114) is an inhibitor of the catalytic activity of HIV-1 protease with potent in vitro antiviral activity against both wild-type and PI-resistant HIV-1 strains. Darunavir has a high genetic barrier to the development of resistance, resulting in continued antiviral activity against a large panel of viruses resistant to currently licensed PIs.

Darunavir has been developed by the sponsor as tablets at different strengths and as an oral suspension. In combination with low-dose rtv as a pharmacokinetic booster and other ARVs, it has shown significant efficacy in treatment-naïve and treatment-experienced patients. Darunavir, in combination with other ARVs, is currently indicated for the treatment of HIV-1 infection in adults and pediatric patients aged 3 years and older, in either a twice daily regimen with rtv or a once daily dosing regimen, with either rtv or COBI. The once daily regimens are approved only for use in treatment-naïve patients and treatment-experienced patients who have no DRV RAMs. COBI-boosted DRV is only approved for use in adults.

Darunavir was first registered in the USA (June 2006) and has obtained marketing authorization in the European Union (EU) in February 2007. As of 23 December 2014, DRV was registered in more than 99 countries around the world. Adverse drug reactions identified during postmarketing experience were: drug hypersensitivity, angioedema, urticaria, osteonecrosis, toxic epidermal necrolysis (TEN), acute generalized exanthematous pustulosis (AGEP), and drug rash with eosinophilia and systemic symptoms (DRESS).

In treatment-naïve and treatment-experienced patients with no DRV RAMs, the recommended dose of DRV is 800 mg taken with a booster once daily and with food. This dose recommendation is generally safe and well tolerated. The majority of the DRV ADRs reported in the Phase 3 studies during treatment with DRV/rtv and NRTIs were mild in severity. In ART-naïve HIV-1 infected adult subjects (343 subjects, total exposure of 1,072 patient years), the most frequent ($\geq 5\%$) ADRs of moderate to severe (grade 2 to 4) intensity with DRV/rtv 800/100 mg once daily were diarrhea, headache and abdominal pain. Only 2.3% of the subjects discontinued DRV treatment due to ADRs. Frequency, type and severity of ADRs in pediatric patients were comparable to those observed in adults.

1.2.2. Cobicistat (Tybost®)

Cobicistat (formerly known as GS-9350) is a structural analog of rtv that has been shown to be a potent inhibitor of cytochrome P450 (CYP) 3A enzymes. Cobicistat has been shown to be a more specific, mechanism-based CYP3A inhibitor than rtv. Cobicistat displays weak to minimal inhibition of other CYP enzymes; it is a less potent inducer of other metabolizing enzymes in

vitro, and has been shown to have less potential for clinically significant drug interactions via non-CYP3A pathways. In addition, COBI is devoid of anti-HIV activity and may have fewer adverse biochemical effects (eg, effect on adipocyte functions such as lipid accumulation) than rtv.

Cobicistat, as a single 150-mg tablet, has been developed by Gilead Sciences, Inc (GSI) and is approved for once daily use in adults as a pharmacokinetic enhancer to increase systemic exposure levels of coadministered drugs metabolized by CYP3A, including PIs such as DRV and atazanavir (ATV) for the treatment of HIV-1 infection. Cobicistat has also been coformulated with other HIV-1 ARV drugs in several FDCs such as DRV/COBI (codeveloped by GSI and the sponsor), ATV/COBI (codeveloped by GSI and Bristol-Myers Squibb), a combination tablet containing EVG boosted with COBI, and FTC + TDF (or E/C/F/TDF, by GSI) for use in HIV-1-infected, ART-naïve patients. As part of these FDCs, COBI has shown to inhibit CYP3A-mediated metabolism of EVG, ATV, and DRV similar to rtv. The FDC DRV/COBI (PREZCOBIX™/REZOLSTA®) has recently been approved in Canada, Europe and the United States, and is indicated in combination with other ARV medicinal products for the treatment of HIV-1 infection in adults aged 18 years or older.

The efficacy and safety of COBI have been established in the pivotal Phase 3 Study GS-US-216-0114 and the supportive Phase 2 Study GS-US-216-0105. Both of these studies were double-blind and active-controlled studies with combination ARV regimens in ART-naïve subjects with HIV-1 infection, and both studies were designed to compare COBI-boosted ATV with rtv-boosted ATV in combination with FTC and TDF. In addition, study GS-US-216-0130 demonstrated the safety and efficacy of COBI with DRV dosed in a once daily regimen combined with a backbone therapy of 2 NRTIs in HIV-1 infected, ART-naïve and treatment-experienced adults with no DRV RAMs.

In the clinical studies to date, COBI 150-mg tablets, dosed daily for up to 60 weeks, were generally well tolerated, did not cause clinically significant toxicities in humans that were identified in nonclinical testing (heart, liver, thyroid abnormalities, and decreased immunoglobulin G levels), and did not potentiate the side effects of the coadministered ARV medications. In Phase 2 clinical studies (GS-US-216-0105 and GS-US-236-0104), small (approximately 12% to 15%) decreases in estimated glomerular filtration rate (eGFR) calculated using the Cockcroft-Gault calculation occurred within the first few weeks of COBI initiation (in GS-US-216-0105, the decreases were comparable to those associated with rtv in the comparator group).

A Phase 1 study of the effect of COBI on eGFR was performed by measuring iohexol clearance in healthy subjects. Results indicated that COBI produces small increases in serum creatinine translating into decreases in eGFR, but not affecting actual GFR, as measured by iohexol clearance. The data suggest that COBI blocks secretion of serum creatinine, resulting in a difference between eGFR and actual GFR, as seen with several other drugs that are currently approved, including trimethoprim and cimetidine. The increase in serum creatinine with COBI occurs within days of drug initiation and is reversible with values returning to baseline within days of cessation of COBI.

1.2.3. Emtricitabine (Emtriva®)

Emtricitabine is an NRTI for the treatment of HIV-1 infection, in combination with other ARVs, in adults and pediatric patients aged 3 months and older. Emtricitabine has been developed by GSI and is marketed as a once-daily capsule (200 mg) and as an oral solution (10 mg/mL). It is a synthetic analogue of the naturally occurring pyrimidine 2'-deoxycytidine. Intracellularly, FTC is phosphorylated by cellular enzymes to form the active metabolite, emtricitabine triphosphate.

Since first marketing authorization in the United States (July 2003), FTC obtained marketing authorization in the EU, and also Argentina, Israel, Switzerland, Mexico, Australia, Japan, New Zealand, and Canada. The registration of FTC for the treatment of HIV-1 infection in adults and pediatric patients less than 18 years of age was supported by an extensive program of clinical studies in healthy subjects and HIV-infected subjects, which provided detailed assessments of its pharmacokinetics, pharmacodynamics, potential drug-drug interactions, and clinical efficacy and safety. Emtricitabine has also been coformulated with other HIV-1 ARV drugs in several FDCs such as EVG/FTC/TDF, E/C/F/TDF, and FTC/TDF (see below).

1.2.4. Tenofovir Alafenamide

Tenofovir alafenamide (also known as GS-7340) is a second generation oral prodrug of TFV, a nucleotide analog that inhibits HIV-1 reverse transcription, developed by GSI. TAF has been coformulated with other ARVs, such as E/C/F/TAF and F/TAF (developed by GSI) and D/C/F/TAF (codeveloped by GSI and the sponsor), for the treatment of HIV-1 infection because of its potential for enhanced distribution of TFV into peripheral blood mononucleated cells (PBMCs) and to lymphatic organs following oral administration. This provides the possibility for using a low dose and to reduce systemic TFV concentrations, resulting in lower potential for adverse effects (including renal and bone toxicity) without compromising antiviral activity. Based on nonclinical data, the clinical safety and resistance profile for TAF is expected to be similar to that characterized for TDF.

Following its release from the TAF prodrug, TFV is metabolized intracellularly to the active metabolite, TFV-diphosphate, a competitive inhibitor of HIV-1 reverse transcriptase (RT), thereby effectively blocking the replication and spread of infectious HIV-1. The *in vitro* activity of TAF against HIV-1 in various human immune cell types is 100- to 600-fold greater than that of TFV and 4- to 6-fold greater than that of TDF.

The term "sponsor" used throughout this document refers to the entities listed in the Contact Information page(s), which will be provided as a separate document.

1.3. Overall Rationale for the Study

The goals of this study are to assess the efficacy and safety of D/C/F/TAF in newly diagnosed HIV-1 infected subjects starting ART in a Test and Treat model.

Thus far, only a few studies have examined Test and Treat models of HIV care. Most studies that have been completed or are ongoing are limited to the developing world, and conducted with regimens that are not recommended by the DHHS Treatment Guidelines.⁹ Differences in screening, healthcare system administration, treatment guidelines, and treatment regimens may

affect the applicability of these studies to newly diagnosed HIV-1 infected subjects in the United States and other developed nations. As the D/C/F/TAF FDC is still being examined in Phase 3 clinical studies, no evidence currently exists using D/C/F/TAF FDC in a Test and Treat model. Given these factors, findings from this study will be used to generate data on the efficacy and safety profile of D/C/F/TAF FDC in newly diagnosed HIV-1 infected, treatment-naïve subjects using a Test and Treat model of care.

2. OBJECTIVES, ENDPOINTS, AND HYPOTHESIS

2.1. Objectives and Endpoints

2.1.1. Objectives

Primary Objective

The primary objective of this study is to assess the efficacy of D/C/F/TAF FDC in a Test and Treat model of care in newly diagnosed HIV-1-infected, treatment-naïve subjects as determined by the proportion of virologic responders defined as having HIV-1 RNA <50 copies/mL at Week 48 (Food and Drug Administration [FDA]-defined intent to treat [ITT] snapshot analysis).

Secondary Objectives

The secondary objectives of this study are:

- To assess virologic and immunologic changes in the study population through 12, 24, and 48 weeks of treatment
- To evaluate the incidence of grade 3 and 4 adverse events, serious adverse events, and premature discontinuations due to adverse events through 24 and 48 weeks of treatment, and during the extension phase
- To evaluate the frequency of discontinuation of D/C/F/TAF FDC due to protocol-specific stopping rules (refer to Section 3.1)
- To assess baseline viral resistance in the study population
- To assess the development of viral resistance in the study population through 24 and 48 weeks of treatment, and during the extension phase
- To assess the proportion of subjects retained in care after discontinuation of study drug before Week 48
- To evaluate the influence of various intrinsic and extrinsic factors on retention in care
- To assess the proportion of subjects lost to follow-up through 24 and 48 weeks of treatment
- To evaluate adherence by pill count to D/C/F/TAF FDC in the study population through 24 and 48 weeks of treatment
- To evaluate adherence by subject self-report, using a 4-day recall period through Weeks 24 and 48
- To describe predictors of suboptimal adherence (<95% adherence by pill count) in the study population

- To assess the HIV Treatment Satisfaction Questionnaire-status version (HIVTSQs) at Weeks 4, 24, and 48
- To evaluate healthcare resource utilization (HRU) and cost and their temporal trends in the study population through 48 weeks of treatment

2.1.2. Endpoints

Primary Endpoint

The primary endpoint of this study is the proportion of subjects who have HIV-1 RNA <50 copies/mL at Week 48 as defined by the FDA snapshot analysis (ITT).

Secondary Endpoints

The secondary endpoints of this study are:

Efficacy

- Change from baseline in log₁₀ HIV-1 RNA viral load at Weeks 2, 4, 8, 12, 24, 36, and 48
- Proportion of subjects who have HIV-1 RNA <50 copies/mL at Week 24
- The change from baseline in CD4⁺ cell count at Weeks 12, 24, and 48

Safety

- Proportion of subjects that required discontinuation after enrollment based on safety stopping rules (refer to Section 3.1)
- Proportion of subjects discontinuing therapy due to adverse events
- Proportion of subjects experiencing grade 3 and 4 adverse events
- Proportion of subjects experiencing grade 3 and 4 laboratory abnormalities

Resistance

- Proportion of subjects meeting resistance stopping rules (refer to Section 3.1), requiring discontinuation of study drug due to baseline resistance findings
- Proportion of subjects with baseline PR, RT, and INI RAMs
- Proportion of subjects developing RAMs and loss of phenotypic susceptibility, when available, upon meeting protocol-defined virologic failure
- Proportion of subjects with protocol-defined virologic failure at Week 24 and Week 48, and during the extension phase

Retention in Care

- Proportion of subjects lost-to-follow-up throughout the 48 weeks of treatment
- Proportion of subjects discontinuing study drug for any reason other than withdrawal of consent prior to Week 48 who have a documented clinic visit with a healthcare provider within 90 days of discontinuing study drug

Adherence

- Adherence rates by pill count at Weeks 4, 8, 12, 24, 36, and 48
- Adherence rates by subject self-report, using a 4-day recall at Weeks 4, 8, 12, 24, 36, and 48

Tolerability/Patient-reported Outcomes

- Mean total scores for the HIVTSQs at Weeks 4, 24, and 48¹²

Healthcare Resource Utilization/Pharmacoeconomics

- The number and duration of hospitalizations, number and type of outpatient visits, number of emergency room visits, and number and type of medications used (both HIV-related and All-cause as assessed by the investigator) throughout the main study period
- Direct medical costs will be calculated in USA dollars based on HRU noted above

Refer to Section 9, Study Evaluation, for evaluations related to endpoints.

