The number of PR mutations (including International AIDS Society-United States of America [IAS-USA] primary and secondary PI RAMs), RT mutations (including IAS-USA nucleoside/nucleotide RT inhibitor [N(t)RTI] RAMs and IAS-USA non-nucleoside RT inhibitor [NN(t)RTI] RAMs), and INI mutations (including IAS-USA primary and secondary INI-RAMs) present will be tabulated based on resistance tests performed at the screening/baseline visit.

The proportion of subjects meeting resistance stopping rules, requiring discontinuation of study drug, based on the findings of screening/baseline resistance testing will be tabulated as part of the interim analysis.

HIV-1 genotype/phenotype will be analyzed from samples of subjects with protocol-defined virologic failure and with HIV-1 RNA ≥ 400 copies/mL.

The number of treatment-emergent PR mutations (including IAS-USA primary and secondary PI RAMs) and RT mutations (including IAS-USA N(t)RTI RAMs and IAS-USA NNRTI RAMs), as well as specific mutations associated with resistance to DRV, FTC, and TAF will be tabulated based on the observed protocol-defined virologic failures through the study period.

Fold change (FC) in 50% effective concentration (EC₅₀) of ARVs will be tabulated. Loss of phenotypic susceptibility may be analyzed dependent on the number of virologic failures and phenotypes available through the study period.

Medical Resource Utilization Analyses

All-cause and HIV-specific HRU during the study period will be summarized overall and by category as the counts per patient per month (PPPM). Monthly average counts per subject will also be calculated to show the temporal trend for each category.

Costs of care will be calculated by assigning costs based on Centers for Medicare & Medicaid Services (CMS) fee schedule to assessed HRU on a per subject per month basis. Descriptive statistics will be calculated to compare the costs of care from baseline to Weeks 12, 24, and 48.

Adherence Analyses

Treatment adherence based on pill count and on subject self-report will be summarized by means of descriptive statistics and frequency tabulations.

Adherence rates will be reported according to the proportion of subjects taking >95%, 80-95% and <80% of study drug as assessed by pill count at study visits at Weeks 4, 12, 24, and 48.

Retention in Care Analyses

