9.2.2. Resistance Determinations

HIV-1 genotype/phenotype resistance testing will be performed at the time points specified in the [Time and Events Schedule](#).

Resistance testing at the screening/baseline visit (Day 1) will be performed utilizing the GenoSure Prime[®] assay. Resistance-associated mutations present at baseline will be reported and include mutations in the domain of PR, RT, and INI.

To investigate the emergence of resistance, the following subjects will be eligible for genotypic/phenotypic resistance testing (PhenoSense GT[®]):

- Any subject who experiences a protocol-defined virologic failure;
- Any subject who discontinues study treatment after Week 12 for any reason and has an HIV-1 RNA value ≥ 400 copies/mL at the last viral load measurement;
- Any subject who has persistent HIV-1 RNA ≥ 400 copies/mL past Week 24 but does not meet the definition of virologic failure.

Baseline phenotyping may be performed retrospectively on subjects with confirmed protocol-defined virologic failure if after virologic failure they showed evidence of reduced phenotypic susceptibility to any of the study drugs. Evaluations may be performed at other time points at the sponsor's discretion.

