10.2. Withdrawal From the Study

A subject will be automatically withdrawn from the study for any of the following reasons:

- Lost to follow-up
- Withdrawal of consent
- Discontinuation of study treatment for any reason
- Subject request to stop study treatment for any reason.

A subject's study treatment **must** be discontinued if:

- The investigator or sponsor believes (eg, that for safety or tolerability reasons (eg, adverse event) it is in the best interest of the subject to discontinue treatment
- The subject becomes pregnant
- The subject meets any of the safety stopping rules (see Section 3.1, Overview of Study Design)

- The subject meets any of the resistance stopping rules (see Section 3.1, Overview of Study Design)
- The subject experiences unacceptable toxicity (as defined in Section 9.8, Toxicity Management)
- The subject develops clinical hepatitis
- Prolonged temporary study treatment discontinuation >4 consecutive weeks
- The study is discontinued at the request of the sponsor, concerned regulatory agency, or Independent Ethics Committee/Institutional Review Board (IEC/IRB)

A subject's study treatment **may** be discontinued if:

- A serious adverse event occurs
- The subject fails to comply with the protocol or study staff requirements
- Intercurrent illness that would, in the judgment of the investigator, affect assessments of clinical status to a significant degree
- The subject starts disallowed treatment, or requires new onset treatment with one of the disallowed medications (please refer to Section 8, Prestudy and Concomitant Therapy)
- The subject experiences protocol-defined virologic failure, shows resistance to study drug(s) upon genotypic and phenotypic resistance testing, and the investigator makes the decision to discontinue study treatment
- The subject experiences persistent HIV-1 RNA ≥ 400 copies/mL after Week 24, that does not meet the protocol-defined virologic failure criteria, but shows resistance to study drug(s) upon genotypic and phenotypic resistance testing, and the investigator makes the decision to discontinue study treatment

Protocol-defined virologic failure is not considered a stopping rule.

If the investigator considers withdrawing a subject from study treatment for one of the above reasons, he/she should contact the sponsor for further discussion and final decision, unless the medical condition requires immediate action that cannot wait contact with the sponsor.

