11.4.2. Resistance Determinations

The number of PR mutations (including IAS-USA primary and secondary PI RAMs), RT mutations (including IAS-USA N[t]RTI RAMs and IAS-USA non-nucleoside RT inhibitor [NN(t)RTI] RAMs), and INI mutations (including IAS-USA primary and secondary INI-RAMS) present will be tabulated based on resistance tests performed at the screening/baseline visit.

The proportion of subjects meeting resistance stopping rules, requiring discontinuation of study drug, based on the findings of screening/baseline resistance testing will be tabulated as part of the interim analysis.

HIV-1 genotype/phenotype will be analyzed from samples of subjects with protocol-defined virologic failure and with HIV-1 RNA ≥ 400 copies/mL.

The number of treatment-emergent PR mutations (including IAS-USA primary and secondary PI RAMs) and RT mutations (including IAS-USA N(t)RTI RAMs and IAS-USA NNRTI RAMs), as well as specific mutations associated with resistance to DRV, FTC, and TAF will be tabulated based on the observed virologic failures through the study period.

Fold change (FC) in 50% effective concentration (EC₅₀) of ARVs will be tabulated. Loss of phenotypic susceptibility may be analyzed dependent on the number of virologic failures and phenotypes available through the study period.

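### Emergent resistance is counted only in protocol-defined virologic failures, although the protocol tests two further groups for it

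*Protocol*

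**What the plan says.** - **Objective (Section 2.1.1):** "To assess the development of viral resistance in the study population through 24 and 48 weeks of treatment", and in the extension. It is not conditioned on failure.
- **Testing (Section 9.2.2, repeated in the synopsis and in footnote o of the Time and Events Schedule):** to study emergence, three groups are eligible for combined genotype/phenotype testing.
  - Group 1: protocol-defined virologic failure.
  - Group 2: "Any subject who discontinues study treatment after Week 12 for any reason and has an HIV-1 RNA value" of at least 400 copies/mL at the last measurement.
  - Group 3: persistent RNA of at least 400 "past Week 24 but does not meet the definition of virologic failure".
- **Endpoint (Section 2.1.2 and synopsis):** "Proportion of subjects developing RAMs and loss of phenotypic susceptibility, when available, upon meeting protocol-defined virologic failure".
- **Samples to be analysed (Section 11.4.2):** "HIV-1 genotype/phenotype will be analyzed from samples of subjects with protocol-defined virologic failure and with HIV-1 RNA" of at least 400 copies/mL.
- **Mutation table:** in the synopsis the emergent mutations "will be tabulated based on the observed protocol-defined virologic failures through the study period". Section 11.4.2 drops the qualifier: "specific mutations associated with resistance to DRV, FTC, and TAF will be tabulated based on the observed virologic failures through the study period".
- **Discontinuation (Section 10.2):** treatment may be stopped in a subject with persistent RNA of at least 400 after Week 24 "that does not meet the protocol-defined virologic failure criteria, but shows resistance to study drug(s) upon genotypic and phenotypic resistance testing".

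**The concern.** The protocol tests three groups for emergent resistance and then reports on one. A subject in group 2 or 3 whose virus acquires mutations on treatment could be tested, found resistant and even discontinued for it, yet appear in neither the named endpoint nor the mutation table. The reported figure would then answer a narrower question than the objective asks.

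This matters for a Test and Treat design. Treatment starts before the baseline genotype is known, and subjects with M184I/V alone may stay in the study (Section 3.1). Emergent resistance is therefore one of the results that readers will look for.

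**Working it through.** The protocol states no figure for emergent resistance, so there is none to reproduce. The check asks whether groups 2 and 3 can fall outside the failure definition, whether other text picks them up, and what an omitted case would do to the result.

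**1. Failure definition (Section 3.1).** All criteria need confirmation at 2 to 4 weeks.
- Nonresponse: less than a 1 log10 fall from baseline and RNA of at least 400, judged at Week 12 only.
- Rebound (a): RNA of at least 50 after confirmed consecutive values below 50.
- Rebound (b): a rise of more than 1 log10 from nadir.

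**2. Group 3 is outside this definition by its own wording, and it can occur.** Take a hypothetical course through every scheduled visit (copies/mL):

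| Baseline | Wk 2 | Wk 4 | Wk 8 | Wk 12 | Wk 24 | Wk 36 | Wk 48 |
|---|---|---|---|---|---|---|---|
| 100,000 | 5,000 | 1,500 | 900 | 800 | 700 | 1,200 | 2,000 |

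- Nonresponse: log10(100,000/800) = 2.10, which is not below 1. Not met.
- Rebound (a): RNA is never below 50. Not met.
- Rebound (b): log10(2,000/700) = 0.46, which is not above 1. Not met.
- RNA is at least 400 at Weeks 36 and 48, so the subject is in group 3.

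The highest Week 12 level that still avoids nonresponse is 10^(baseline log10 − 1): 10,000 copies/mL for a baseline of 5.0 log10, 31,623 for 5.5 and 100,000 for 6.0. A subject who passes Week 12 in this way and never suppresses can become a failure later only through rebound (b).

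**3. Group 2 is outside when failure is not confirmed.** Confirmation takes 2 to 4 weeks. Under Section 10.2, stopping treatment withdraws the subject, the discontinuation visit is due within 1 week, and the 30-day visit is only for ongoing adverse events. A rise first seen at the last visit can stay unconfirmed.

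**4. Does other text bring these subjects in?**
- Section 9.2.1 makes detected resistance part of the efficacy analysis but names no count.
- The EC50 fold-change sentence in Section 11.4.2 has no failure restriction, but it gives phenotype data and is neither the endpoint nor a mutation table.
- Section 11.9 allows resistance to be summarised or listed without a failure restriction, but only for the extension.
- The wording of the table in Section 11.4.2 does not help. Section 3.1 gives one definition of failure, and group 3 is stated not to meet it.

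**5. Effect of an omitted case.** The counts below are assumptions, because the protocol gives no frequencies for groups 2 and 3.

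If all treated subjects are the denominator (N = 100), with 0 cases among failures and k cases outside, the proportion is k/100 with an exact (Clopper-Pearson) 95% CI:

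| k | Reported, failures only | All tested groups | 95% CI for all tested groups |
|---|---|---|---|
| 0 | 0% | 0% | 0 to 3.6% |
| 1 | 0% | 1% | 0.03 to 5.4% |
| 2 | 0% | 2% | 0.2 to 7.0% |

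If the denominator is failures or tested subjects, the direction depends on the added subjects:
- 0/5 = 0% becomes 1/7 = 14.3% if 1 of 2 added subjects has resistance.
- 2/4 = 50.0% becomes 2/7 = 28.6% if none of 3 added subjects has it.

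**The case against.** A protocol may test more widely than its named endpoint. Testing also serves care, since the resistance report goes to the next provider, and the endpoint states its condition openly. The study tests no hypothesis. Section 11 leaves details to the statistical analysis plan, which could add tables. Testing in group 3 is partly discretionary: Section 3.1 makes it conditional on being appropriate, whereas footnote o of the Time and Events Schedule says it will be done. What counts as persistent is not defined. A pooled proportion would then depend partly on investigators' choices, whereas a failure-based endpoint is more uniform. Finally, no size is shown.

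Part of this stands. The size is unknown, uneven testing is a real caveat to pooling, and table layout belongs in the analysis plan. The limit to the main period is also inferred: the table sentence refers to the study period, and Section 11.9 treats the extension separately.

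The rest does not remove the point. Section 9.2.2 gives the emergence of resistance as the purpose of testing all three groups, and the objective covers the study population. The restriction is written into the protocol's endpoint and table, so it is not a detail left open. Reporting by reason for testing, with the number eligible but untested, deals with uneven testing.

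**Conclusion.** The concern holds. Followed as written, the protocol leaves emergent resistance found in the main period outside confirmed failure out of both its only emergent-resistance endpoint and its treatment-emergent mutation table.

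The effect is probably small. The Background (Section 1.2) reports almost no emergent darunavir mutations in treatment-naive failures on boosted darunavir, though it gives no corresponding result for emtricitabine or tenofovir alafenamide. In the main period group 3 can arise at only two scheduled visits, Weeks 36 and 48. With all treated subjects as denominator (assumed N = 100), omission can only lower the proportion, by 1 percentage point per case. With a denominator of failures or tested subjects, no consistent direction can be claimed. The primary endpoint and the sample size are untouched. It is a correction that should be made, with medium confidence in its practical weight.

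**What to change.** In the synopsis and Sections 2.1.2 and 11.4.2:

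- Base the emergent-resistance endpoint and the treatment-emergent mutation table on all subjects with a post-baseline resistance result under Section 9.2.2, by reason for testing and pooled.
- Keep the result for protocol-defined failures as a subset.
- State the denominator, and show the numbers in the ITT population, tested, and eligible but untested.

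The cost is wording in three places and one extra table. It uses tests that the protocol already provides for and changes no clinical rule. The reported resistance figure may be slightly less favourable.
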